Atomoxetine and Oxybutynin in Obstructive Sleep Apnea (ATOSA)

NCT02908529

This study is part of the protocol:

Pharmacologically improving the pharyngeal muscle activity during sleep: implications for the novel treatment of obstructive sleep apnea, approved on 08/24/2014

This protocol version is dated 6/26/2017

DETAILED PROTOCOL (version approved 6/26/2017)

Title: Pharmacologically improving the pharyngeal muscle activity during sleep: implications for the novel treatment of obstructive sleep apnea.

Principal Investigator: [name], PhD

I. BACKGROUND AND SIGNIFICANCE

Obstructive sleep apnea (OSA) is characterized by repetitive collapse or ‘obstruction’ of the pharyngeal airway during sleep. Over the last decade, and particularly in the last few years, research has shown that a number of pathogenic factors, or traits, contribute to the development of OSA (1-4). These include: 1) an anatomically small, collapsible upper airway; 2) an oversensitive respiratory control system leading to ventilatory overshoots and undershoots, i.e., instability; 3) a loss of pharyngeal muscle tone or responsiveness during sleep; and 4) a low respiratory arousal threshold, i.e., premature arousal to respiratory stimuli.

Despite our improved understanding of the pathogenesis of OSA, it has not led to improved therapy. Continuous positive airway pressure (CPAP) is still the only viable treatment for most patients, and it is usually effective because it mechanically splints the upper airway open. The problem, however, is that many patients cannot use CPAP because they find it intolerable. This represents a significant health concern, as OSA is known to cause a number of adverse cardiovascular (5-12), neurocognitive (13), and daytime functioning (14) consequences.

One possible approach to finding alternative treatments for OSA is to continue searching for a single drug or agent that, like CPAP, has a large enough effect size to override the various causes of OSA. This approach has proven difficult, and while we hold out hope for such a drug, in the meantime we have adopted another (possibly equally effective) tactic, which is to target the relevant upstream mechanisms or individual traits with one or more drugs in an individual patient. The rationale for this approach is that non-CPAP therapies have tended to have small effect sizes and proven, by themselves, marginally effective at fully correcting OSA in many patients. Another reason stems from the manner in which most major medical disorders are treated. Rarely is a single drug used to treat, for example, congestive heart failure, hypertension, asthma, etc., unless the condition is mild. In our view, a similar approach should be taken for managing OSA.

Regardless of whether single or multidrug therapy is ultimately used, the search for alternative treatments has been lacking a very important ingredient – a drug to stimulate the pharyngeal muscles. While a host of oral devices and surgeries have been developed to address the anatomical predisposition to collapse, and our group has made significant headway in dealing with ventilatory control sensitivity (15, 16), drugs that activate the pharyngeal muscles are needed. Interestingly, new research in animals has improved our understanding of the state-dependent neurotransmitters involved in pharyngeal muscle activation during sleep. Importantly, the loss of noradrenergic activity is now thought to play the key role in the sleep-related hypotonia of pharyngeal muscles.

Chan and colleagues (17) showed in rats that the noradrenergic antagonist terazosin substantially reduced genioglossus (a major muscle of the upper airway) activity (EMG_{GG}) during wakefulness and produced REM-like atonia during NREM sleep, illustrating the importance of noradrenergic mechanisms. Other studies (18, 19) also support the notion that progressive withdrawal of noradrenergic tone, from wakefulness to NREM and REM sleep, is the major mechanism causing sleep-related pharyngeal hypotonia. While noradrenergic withdrawal is thought to be the main cause of pharyngeal hypotonia in NREM sleep, there are additional mechanisms that cause further reduction in REM sleep. Chan and colleagues (17) failed to reverse REM atonia with alpha-1 receptor agonists applied to the hypoglossal nucleus, suggesting that another, possibly inhibitory, mechanism is at work. Horner and colleagues have identified this inhibitory process as muscarinic by demonstrating restoration of EMG_{GG} activity during

DETAILED PROTOCOL (version approved 6/26/2017)

REM sleep with the muscarinic antagonist scopolamine (20, 21). More recently, these researchers found that the multiple state-dependent adrenergic, serotonergic and muscarinic systems produce suppression of EMG_{GG} activity during sleep via a convergent ionic mechanism: increased potassium conductance. Blockade of potassium channels has been shown in mice to be capable of reactivating the pharyngeal musculature throughout sleep (22).

However, due to the only recent identification of this process, there has not yet been an attempt to stimulate the pharyngeal muscles with noradrenergic drugs in sleeping humans. Now, more than ever, the stage has been set for stimulating the pharyngeal muscles across both NREM and REM sleep.

II. SPECIFIC AIMS

To determine the effect of noradrenergic and antimuscarinic drugs on OSA severity and pharyngeal muscle activity during sleep. We hypothesize that existing drugs with these neurotransmitter profiles could (partially) restore pharyngeal muscle activity in humans during sleep.

Specifically, we will test this hypothesis by assessing:

The effect of the combination of atomoxetine (a norepinephrine reuptake inhibitor) plus oxybutynin (an antimuscarinic drug) on the apnea-hypopnea index (AHI) and EMG_{GG} during sleep.

III. SUBJECT SELECTION

We will recruit a group of OSA patients to determine what effect these drugs will have on improving the patient's OSA severity.

a) Obstructive Sleep Apnea Patients (n=30): Patients with OSA will be recruited from our clinical sleep laboratory at Brigham and Women's Hospital, as well as from our existing database of OSA patients. These individuals will be otherwise healthy (except for well-controlled hypertension; defined as systolic blood pressure <140 mmHg and diastolic <90 mmHg) with no active medical problems and on no medications that could affect respiration or muscle control. All will be 21-65 years of age. Both men and women will have an apnea-hypopnea index (AHI) >10 events/hr during supine NREM sleep. These individuals will be recruited to encompass a large range of AHI's (from 10 to >60/hour). Approximately 30 patients will be recruited for this protocol.

Exclusion criteria:

- Any medical condition other than well controlled hypertension.
- Any medication known to influence breathing, sleep/arousal or muscle physiology.
- Claustrophobia.
- Inability to sleep supine.
- Allergy to lidocaine or atomoxetine/oxybutynin,
- Benign prostatic hyperplasia or urinary retention, which can be exacerbated by antimuscarinic medications.
- Individuals with underlying cardiac disease, such as arrhythmias.
- Individuals taking psychiatric medications, or any of the studied medications for medical care.
- History of seizures
- History of moderate or severe renal impairment
- For women: Pregnancy.

We will consider all applicants regardless of gender, race, color, creed, or national origin.

DETAILED PROTOCOL (version approved 6/26/2017)

IV. SUBJECT ENROLLMENT

Subjects will be recruited through email, telephone, newspaper, and or bulletin advertisements. Men and women with OSA will be recruited from a pool of patients being newly diagnosed with OSA and currently followed in our outpatient clinic or by advertisement in the sleep disorders clinic. Only patients who have stated in the initial clinical questionnaire that they are interested in hearing about research studies will be contacted by phone. Should the subject be interested in the study, they can call the study physician or coordinator to inquire about study participation. We will also recruit from our existing database of research participants.

Subjects who respond will be given a thorough review of the risks, discomforts, potential benefits to the study and their expected involvement using a prepared script approved by our Institutional Review Board. Subjects will be given a copy of the informed consent and allowed a minimum of 24 hours to review the information and make a decision on study participation. During this time, the subject will have the opportunity to discuss the research with his/her primary care physician or clinician. The study investigators will be available to answer any questions should any arise. Informed consent will be obtained by the Principal Investigator or an experienced co-investigator prior to participation in the study. The opportunity to talk to a licensed MD (who is readily available at the time of consent, and available overnight at the hospital) will be offered in each case. Subjects will have more than 24 hours to consider participating in the study. Any consent issues / problems will be reported to the PHRC in real time rather than waiting to report at the time of Continuing Review

Inclusion and exclusion criteria will be carefully assessed prior to enrollment. Assuming subjects meet the inclusion criteria, they will begin the protocol by scheduling their overnight studies in the clinical/physiology laboratories. Subjects will be informed that they may withdraw from the study at any point, with no impact on their ongoing care. We have not previously had difficulty enrolling participants into similar studies performed in our laboratory.

If the data collected will be considered insufficient by the PI or by the co-investigators, the subject will be asked to repeat the whole study or a part of it without signing a new informed consent form.

After completing the main study, patients enrolled will be asked to perform two extra study nights in which atomoxetine and oxybutynin alone will be administered if they showed an improvement in EMG_{GG} activity and OSA severity in the night in which they took the combined therapy.

V. STUDY PROCEDURES

The effect of Atomoxetine and Oxybutynin on OSA severity and genioglossus muscle activity (EMG_{GG})

Protocol:

Two overnight sleep studies will be performed approximately 1 week apart: a placebo night and a Atomoxetine-Oxybutynin (ato-oxy, 80-5 mg PO) night, in double-blinded randomized control design. For each night, the subjects will arrive at the sleep laboratory at approximately 7:00pm. A physician will complete a complete physical and medical history. The placebo or ato-oxy will be administered 30 minutes before lights out. At least 15 minutes of quiet wakefulness will be recorded to quantify the subject's awake EMG_{GG} activity. Subjects will then be allowed to fall asleep during which we will assess EMG_{GG} activity throughout the rest of the evening (see below for details).

DETAILED PROTOCOL (version approved 6/26/2017)

Measurements and equipment:

Subjects will be instrumented with standard polysomnography (PSG) recording sensors. Sleep stage and arousals will be measured with electrodes pasted on to the scalp, face, chin and chest (EEG, EOG, EKG, chin EMG). Paste-on EMG electrodes will be placed over the anterior tibialis muscle to detect leg movements. Respiratory effort belts will be placed around the chest and abdomen to measure breathing movements. Oxygen saturation will be measured continuously with a pulse oximetry probe placed on either the fingertip or earlobe. Snoring will be detected with a small microphone positioned over the suprasternal notch. Body position will be recorded with a sensor taped to the thoracic belt. Each of these devices is standard for diagnostic PSG and should not be uncomfortable.

One nostril and the back of the throat will be anesthetized with 4% lidocaine; only 2–3 ml (80–120 mg) of lidocaine is used. One small, flexible pressure-tipped catheter (Millar) will then be inserted through the anesthetized nostril until the tip of the catheter is located just above the epiglottis (or in the esophagus) by visual inspection through the mouth. This catheter is used to assess upper airway negative pressure and to calculate airflow resistance both awake and during sleep. In case of an esophageal catheter, after the visual inspection of the mouth, the patient will be required to swallow several times and the catheter will be advanced slowly to the lower third of the esophagus.

Electromyogram activity from the genioglossus (EMG_{GG}) muscle (a major upper airway dilator muscle) may also be recorded using unipolar intramuscular electrodes as described in our previous studies (1, 23, 24). Two 25 gauge needles containing 30 gauge, Teflon-coated stainless steel wires are inserted into the muscle after topical anaesthesia with 4% lidocaine. A maximum of 2 mls of lidocaine will be used for needle insertion. If the patient cannot tolerate needle insertion once the maximum dose of lidocaine has been applied, then the procedure will be stopped. The needle is immediately removed leaving the wire in place. Both electrodes are referenced to a single ground producing a bipolar recording. GG needle placement is as follows: The muscle is approached through the floor of the mouth with each needle being inserted about 3-5 mm lateral to the frenulum and about 12-15 mm into the body of the genioglossus near its insertion into the mandible. Once the electrodes are placed, the EMG signal is amplified, rectified, and integrated on a moving time average basis with a time constant of 100 msec (CWE Incorporated).

Tests performed during wakefulness.

The patients, with the described monitoring equipment in place, will undertake two tests before going to sleep for the night, although some of the testing may not be performed in all subjects depending on availability of equipment, scheduling issues and willingness of the subject to undergo all of the testing.

Upper airway muscle activity during wakefulness

The subject will be asked to perform several maneuvers to assess the activity of the GG during wakefulness. The maneuvers include a maximal tongue protrusion, inspiration against a closed airway, swallow and maximum voluntary ventilation. Each of these maneuvers will be repeated 3 times.

After these test during wakefulness, the subjects will be given ato-oxy (80-5 mg PO) /placebo to take and the patient will be asked to sleep in the supine position for as much time as possible.

As much data will be recorded from NREM and REM sleep as possible over the night. Following completion of the study, all equipment will be removed, and the subject will be able to sleep in the laboratory free from equipment for the rest of the night. Alternatively, if the subject feels alert enough to leave, they may do so.

Data Analysis:

DETAILED PROTOCOL (version approved 6/26/2017)

Sleep stages, arousals and respiratory events will be scored by a registered polysomnographic technologist blinded to the treatment allocation according to the American Academy of Sleep Medicine recommended criteria.

Muscle activity will be quantified using standard procedures described in our previous studies (1, 23, 24). Briefly, the raw EMG_{GG} signal will be rectified and smoothed with a 100 msec window. The peak phasic, as well as tonic, activity of the smoothed signal will be identified for each breath. Data from quiet wakefulness (free of swallowing and movement artifacts) will be averaged to determine the peak phasic and tonic activities during this state. The same will be done for stable NREM and REM sleep (free of arousals and other artifacts). Pharyngeal muscle responsiveness will be determined by calculating the slope and intercept of the esophageal pressure versus muscle EMG relationship.

Reimbursement

Subjects will receive \$100/night for participation in each overnight study (TOTAL = \$200). Reimbursement for parking expenses will be provided.

If the subjects will repeat a part or the entire protocol because of insufficient data collection, they will be reimbursed \$100 for any extra night.

If the subjects will take part to the additional nights on atomoxetine and oxybutynin alone, they will be paid \$100/night (total \$400).

VI. BIOSTATISTICAL ANALYSIS

Sample size: Based on previous data from the study of the noradrenergic drug desipramine in OSA patients, 20 patients will enable us to detect a reduction in AHI of $50\pm75\%$ (80% power, alpha 0.05), primary outcome. 20 patients will also enable us to detect a $100\pm150\%$ increase in genioglossus activity (80% power, alpha 0.05), secondary outcome. Accounting for a 20-50% failure rate of these kind of physiology studies we anticipate that we may need to enroll up to 30 patients to conclude the study

Variables of interest will be compared using a Wilcoxon matched-pairs signed rank test, with a p-value <0.05 considered statistically significant. To compare the effect of placebo, ato-oxy, atomoxetine alone and oxybutynin alone in the participants who will perform 4 study nights, we will use the Friedman's test with a post-hoc analysis (Wilcoxon) in which each treatment will be compared to placebo; the post-hoc analysis will be conducted with Bonferroni correction (p-threshold=0.017).

VII. RISKS AND DISCOMFORTS

We believe that the risks associated with participation in this study are minimal. All study procedures have been conducted in our laboratory without serious incident. Anticipated risks and discomforts are listed below:

1. The equipment used for assessing sleep (paste on electrodes) is standard and poses no risk. The electrodes may be mildly uncomfortable and could cause some sleep interruption. Thus subjects may feel somewhat tired the day following this study.

DETAILED PROTOCOL (version approved 6/26/2017)

2. Pharyngeal/esophageal Pressure Catheter: Inserting the pressure catheter through the nostril and into the pharynx may be uncomfortable and could cause gagging or even vomiting. The anesthetized and fasting state substantially reduces the risk of discomfort or complications. As the subject will have a catheter in his/her pharynx and a nasal mask in place, the risk of aspiration must be considered. However, this has never been encountered after hundreds of similar studies. The catheter, once in place, does not gag the subject and the mask can easily be removed. Overall, the risk of aspiration is minimal.
 - i. Lidocaine. If the subjects have any history of lidocaine allergy, they will be excluded from the study. Excessive use of lidocaine can cause seizures, but this is reported with much higher doses than will be utilized in this study. However, subjects will be informed that lidocaine has an unpleasant taste.
3. Intramuscular EMG Determination: Needle insertion may be painful although the mucosa is topically anesthetized with lidocaine. We have found this pain to be similar to venipuncture and well tolerated. Discomfort is minimal once the needle is removed and the wire is left in place. A small amount of bleeding and/or a small bruise may occur. Both the needles and wires are sterilized. However, intramuscular or surface infection could occur, as it is impossible to sterilize the inside of the mouth. We have never encountered this problem or heard of it occurring elsewhere. There may be some residual soreness in the tongue for several hours after the wires are removed.
4. Oxybutynin: The common side effects are related to the anticholinergic effect on parasympathetic postsynaptic receptors: dry mouth, throat, and nasal passages in overdose cases progressing to impaired speech, thirst, blurred vision, sensitivity to light, constipation, difficulty urinating, and tachycardia. Other effects of overdose include flushing and fever, as well as excitement, restlessness, hallucinations, or delirium.
5. Atomoxetine: Side effects include alopecia, dry mouth, tiredness, irritability, nausea, decreased appetite, constipation, dizziness, sweating, dysuria, sexual problems, decreased libido, urinary retention or hesitancy, increased obsessive behavior, weight changes, slowed growth in children, palpitations, increases in heart rate and blood pressure.

VIII. POTENTIAL BENEFITS

Although it is unlikely that there will be any direct physical benefit to the subjects from participating in this study, we will make known to each subject, if requested, some of the information we have gathered from this physiologic testing. This study provides a unique opportunity to gain insight into the specific mechanisms by which these novel drugs may improve upper airway muscle function. The results may, in the future, lead to improved strategies for the treatment of sleep apnea. However, if previously unknown abnormalities of sleep and breathing are encountered, this information will be passed onto the subject. Results can be forwarded to the primary care physician or clinician at the request of the subject.

IX. MONITORING AND QUALITY ASSURANCE

We will follow the Data and Safety Monitoring Plan included as an attachment. As this study is a physiological investigation, a formal Data and Safety Monitoring Board will not be implemented. The PI will be responsible for monitoring safety and quality assurance. Additionally, the ongoing

DETAILED PROTOCOL (version approved 6/26/2017)

results, problems, and limitations of the study will be presented on a regular basis to the investigators in the Division of Sleep Medicine. Any adverse events will be promptly reported to the Human Research Committee for review according to HRC guidelines.

Adequacy of Protection Against Risks

All of our laboratory personnel involved in the research of human subjects have completed the required institutional program for education in the protection of human research participants and their confidentiality. The institutional educational program consists of the review of regulatory and informational documents pertaining to human-subject research, passing a test demonstrating knowledge of the ethical principles and regulations governing human-subject research and signing a statement of commitment to the protection of human subjects.

All electronic data will be stored on secure computers under password protection with no access allowed to individuals outside of our research team. All paper data will be stored under lock and key with access only given to the study staff.

Protection Against Risks

We believe that all possible safeguards are in place to minimize the risk. However, several steps will be taken to insure patient comfort and safety. We will work with our IRB to come up with a safety monitoring plan to minimize risk and discomfort. This will include:

- Reporting any complications of our studies immediately to the IRB.
- Appoint a safety officer ([name]) who will work with our physicians and technicians to maximize safety and comfort.
- Our study coordinator will call each subject 2-3 weeks after the study to determine if any problems resulted from the study.

The study coordinator will meet with the safety officer and PI monthly (and as needed) to go over any complaints or problems. The safety officer will call the patients with problems directly to verify important issues. If problems are identified, the protocol will be adjusted as needed. Based on conversations with the NIH and the NHLBI policy (<http://www.nhlbi.nih.gov/funding/ethics.htm>), we will not require a formal data safety monitoring board. However, we do have a thorough data safety monitoring plan whereby our safety officer will review all adverse events in order to classify them as serious adverse events, minor adverse events, and whether they are anticipated or unanticipated, and study related or unrelated as per our IRB rules and the NHLBI policy. The medical monitor will be an academic physician with considerable experience in clinical research but not involved in our research program or a co-investigator in any of our studies ([name]). The medical monitor will strictly adhere to the following definitions:

Definitions

Definitions are per January 2007 OHRP *Guidance on Reviewing and Reporting Unanticipated Problems Involving Risks to Subjects or Others and Adverse Events, OHRP Guidance*, <http://www.hhs.gov/ohrp/policy/AdvEvntGuid.htm>

Adverse Event (AE): any untoward or unfavorable medical occurrence in a human subject, including any abnormal sign (for example, abnormal physical exam or laboratory finding), symptom, or disease, temporally associated with the subject's participation in the research, whether or not considered related to the subject's participation in the research.

DETAILED PROTOCOL (version approved 6/26/2017)

Serious adverse event (SAE): any adverse event that:

- Results in death
- Is life threatening, or places the subject at immediate risk of death from the event as it occurred
- Requires or prolongs hospitalization
- Causes persistent or significant disability or incapacity
- Results in congenital anomalies or birth defects
- Is another condition which investigators judge to represent significant hazards

Unanticipated Problem (UP): any incident, experience, or outcome that meets all of the following criteria:

- unexpected, in terms of nature, severity, or frequency, given the research procedures that are described in the protocol-related documents, such as the IRB-approved research protocol and informed consent document; and the characteristics of the subject population being studied;
- related or possibly related to participation in the research, in this guidance document, possibly related means there is a reasonable possibility that the incident, experience, or outcome may have been caused by the procedures involved in the research;
- suggests that the research places subjects or others at a greater risk of harm (including physical, psychological, economic, or social harm) than was previously known or recognized.

Adverse Events (FDA) versus Unanticipated Problems (OHRP)

- All adverse events are not necessarily unanticipated problems
- All unanticipated problems are not necessarily adverse events
- Some events may be both

DETAILED PROTOCOL (version approved 6/26/2017)

X. REFERENCES

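### Does letting the investigators order repeat nights for insufficient data inflate the type I error for the primary AHI comparison?

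*Combined protocol and SAP*

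**What the plan says.** Section IV (Subject Enrollment) contains the repeat rule: "If the data collected will be considered insufficient by the PI or by the co-investigators, the subject will be asked to repeat". The patient may be asked to "repeat the whole study or a part of it without signing a new informed consent form", so a single night can be redone. The Reimbursement paragraph of Section V gives the ground again: "If the subjects will repeat a part or the entire protocol because of insufficient data collection, they will be reimbursed". No numerical criterion, cap or deadline is given, and no text says whether the original or the repeat recording supplies the AHI.

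Three other statements bear on the point.

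- Section V, Protocol: the two main nights are run "in double-blinded randomized control design".
- Section V, Data Analysis: sleep and breathing are "scored by a registered polysomnographic technologist blinded to the treatment allocation".
- Section IV, final paragraph: once the main study is finished, patients are offered two single-drug nights if they improved in genioglossus activity and "OSA severity in the night in which they took the combined therapy".

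Section VI names AHI as the primary outcome, plans for 20 patients, and compares the nights with a Wilcoxon matched-pairs signed rank test at 0.05.

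**The concern.** An open-ended power to repeat a night can be used selectively. The protocol names only the scoring technologist as blinded, and the technologist does not order repeats. Someone must also link each patient's result to the combination night in order to offer the extra nights, and the text does not say that repeats are settled before that link is made. Blinding might also be imperfect. Section VII lists dry mouth for both drugs and, for atomoxetine, "palpitations, increases in heart rate and blood pressure", while the EKG is recorded all night.

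If the person deciding knew or guessed the allocation as well as the AHI, disappointing drug nights could be redrawn while disappointing placebo nights were left alone. With about 20 pairs, a few such repeats would move the primary test toward the drug.

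**Working it through.** **Inputs.** From Section VI: n = 20 pairs, signed-rank test, alpha 0.05 (taken as two-sided), planned effect 50% with SD 75%. Assumed, because the documents give no figure: the number of repeats k, how the repeated nights are chosen, and how accurately the allocation can be guessed. The 20–50% failure rate in Section VI is not a repeat rate.

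**The plan's own figure.** The standardised effect is 50/75 = 0.667. The normal approximation gives n = (1.960 + 0.842)²/0.667² = 17.66, so 18. The paired t-test with n = 20 has noncentrality 0.667 × √20 = 2.98 and power 80.7%. The stated 20 is reproduced and is not in dispute.

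**Reference level.** For n = 20 the rank sum has maximum 20 × 21/2 = 210. The two-sided 5% test rejects when W ≤ 52 or W ≥ 158. Its exact size is 4.84%.

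**Decision blind to allocation.** Under the null, randomisation makes the drug and placebo labels exchangeable within a patient. A repeat rule that cannot see the labels treats both nights alike, so each paired difference stays symmetric about zero and the signed-rank test keeps its size. This holds even if the rule looks at the AHI. Simulation agrees. When the higher-AHI night is redrawn in the k most discrepant patients (k = 1 to 4), rejection is 4.8–4.9%, whether the repeat replaces the original or the lower recording is kept.

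**Decision made with allocation known.** The simulation draws null normal AHI values with independent night noise, 100,000 to 200,000 runs per case, and the repeat replaces the original:

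| Drug nights repeated (of 20) | Random among unfavourable | The worst k |
|---|---|---|
| 1 | 5.3% | 6.2% |
| 2 | 6.2% | 8.1% |
| 3 | 7.4% | 10.2% |
| 4 | 8.7% | 12.5% |

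The last column requires ranking all 20 patients before choosing, whereas repeats would ordinarily be decided one patient at a time.

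**Allocation only guessed.** Repeating the worst 1, 2 or 4 believed drug nights gives 5.1%, 5.4% and 6.1% at 70% accuracy, and 5.7%, 6.9% and 9.7% at 90%.

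**Which condition the protocol describes.** Section V calls the trial double-blinded, and the ordinary reading of that term includes the investigators who order repeats. The Reimbursement text makes failed collection the ground. That fits a study with a pharyngeal or esophageal catheter, intramuscular wires and an expected 20–50% failure rate. The extra-night selection follows the main study, and a repeat of the whole or part of the study naturally belongs to the main study. Followed as written, the protocol falls under the blind case, at 4.8–4.9%.

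**The case for a change.** The strongest counter-argument is that the choice of recording is open even with perfect blinding. A night can fail for genioglossus EMG yet give a scorable AHI, and repeating it leaves two AHI values for one treatment. With allocation known and 30% of patients repeated, the choice matters: type I error is 5.7% if the recordings are averaged, 9.8% if the repeat replaces the original, and 14% if the lower is kept. Less favourable assumptions go further. If the whole study is repeated in the 4 worst patients at 90% guessing accuracy, the error reaches 18.6%. If every unfavourable drug night is repeated and the lower value kept, it reaches about 34%.

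These figures are sound as conditional statements. All of them, however, require allocation to be known or guessed. Without that, keeping the lower recording costs nothing in type I error. Picking recordings patient by patient after the code is opened would also be a breach of the blind, and the protocol does not provide for it.

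The possible routes to unblinding are inferred. Section VII lists side effects without rates, and nothing in the documents shows that dry mouth or heart rate reveals the allocation here. It is true that the text does not expressly require repeats to be settled before a patient's code is opened, or say who holds the code. That part of the objection stands as missing detail.

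**Conclusion.** No change to the plan follows. Two details are unwritten: a criterion for insufficiency, and which recording supplies the AHI. Under the stated double-blind design neither moves the type I error from about 4.8%. Inflation appears only if the person deciding knows or guesses the allocation. With allocation known, it is then about 5–9% for 1 to 4 randomly chosen unfavourable drug nights out of 20, and up to about 12.5% if the worst four are picked. More extreme assumptions give more, but the documents support neither the repeat counts nor the unblinding.

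Analysts would fill the gap in the ordinary way. They would judge sufficiency blind and on recording quality, separately for the sleep recording and the EMG, and before that patient's code is opened. The repeat would keep its allocation, and the first recording adequate for AHI would be analysed. This conclusion rests on double-blind covering the investigators who order repeats, and on repeats being part of the main study. Both are the natural readings of Sections IV and V.
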